The primary endpoints are visual analog scale (VAS) ratings of the perceived intensity of itch sensation elicited by epicutaneous application of cowhage spicules (non-histaminergic itch) on the volar aspects of the forearms comparing skin pretreated with vehicle cream with the KeAmLi-combination. Ratings will be plotted vs. time to generate a temporal itch intensity graph and the area under the curve (AUC) will be calculated for each subject. The secondary study endpoints are the individual itch peak intensity, itch peak time, and itch time duration comparing skin pretreated with vehicle cream with ketamine, amitriptyline, lidocaine, and KeAmLi-combination.

The exploratory outcomes (for all experimental interventions vs. the vehicle condition) are:

- Warmth detection threshold (°C needed to perceive warmth sensation)
- Heat pain threshold (°C needed to perceive heat pain)
- Mechanical detection threshold (mN needed to perceive touch)
- Mechanical pain threshold (mN needed to perceive pain)
- Development of hyperknesis (NRS ratings of itch evoked by touch before vs. after cowhage provocation)

10) **Procedures Involved***

At the beginning of the first session, subjects will be asked to fill out an informed consent, and a form for demographic information including health information. They will also be asked if they have taken any allergy or pain medicine during the past 24 hours. If so they will be asked to come back at a later time since these drugs might interfere with the study. Females of childbearing potential will undergo an hCG pregnancy test. Finally, subjects will receive instruction on the use of the visual analog scale for rating the intensity of itch sensation. Below is a short procedural overview of the proposed study this is followed by sections introducing in details each of the methods applied.

Subjects will be seated comfortably in a chair with both arms resting on armrests or on a pillow. Using a block-randomized design, we will deliver either topical vehicle (PCCA Lipoderm[®]), topical ketamine 10%, topical amitriptyline 5%, lidocaine 5% or KeAmLi-combo (ketamine 10%, amitriptyline 5%, and lidocaine 5%) to four 4 x 4 cm predefined skin areas on the ventral forearms over two study visits. The 1st visit will involve applying 3 of the 5 treatments (randomized), to 3 of the 4 designated test sites in a randomized manner. The 2nd visit will involve applying the

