To assess mechanical detection thresholds standardized, CE-approved and commercially available von Frey filaments stimulators (North Coast Medical, Stoelting, CA, US) are used. The set consists of 20 calibrated nylon filaments with bending forces from 0.078 mN to 2.9 N (with slightly increasing exerted force surface). Starting with the lightest filament each probe is applied perpendicularly to the skin area for 1-2 seconds with a soft “landing” and removal in an ascending/descending order. The stimulators are designed to detect the mechanical detection threshold (MDT), which is considered the perceptual correlate of cutaneous A β -fiber sensitivity. The final threshold is the geometric mean of five series of ascending and descending stimuli. The quantitative sensory assessment of MDT is based on the standardized and thoroughly tested methodology developed by the German Association for the Study of Neuropathic Pain (DFNS) and follows the published protocol^{39,44}. Due to the completely non-invasive nature of the procedure it is not associated with any risks.

Mechanical pain thresholds (The Pinprick, MRC, Germany)

To test mechanical pain sensitivity standardized, CE-approved and commercially available pinprick stimulators (The PinPrick, MRC, Germany) are used. This set consists of 7 pins with exponentially increasing force increments from 0.8 mN to 512 mN (0.8, 1.6, 3.2, 6.4, 128, 256, and 512 mN). The pinprick stimulators have a 0.2 mm blunted tips designed to deliver a sharp needle-like stimulus without penetrating the epidermis. Starting with the lightest (0.8 mN), each stimulator is applied in an ascending/descending order at a rate of 2s on, 5s off until the first perception of sharpness/pain is reached. This is denoted the mechanical pain threshold (MPT) and represents function of mechano-receptive C- and A δ -nociceptors. The final threshold is the geometric mean of five series of ascending and descending stimuli. The quantitative sensory assessment of MPT is based on the standardized and thoroughly tested methodology developed by the German Association for the Study of Neuropathic Pain (DFNS) and follows the published protocol^{39,44}.

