- 3. Sensory testing of heat pain thresholds.** Heat pain will be assessed using a thermode probe raising the temperature of circulating water from 32°C up to 50°C. Since we only assess the pain perception threshold (i.e. the first temperature at which pain is experienced) this heat pain is marginally unpleasant and only persists for a few seconds. If the pain is unbearable, the thermode can be immediately removed to alleviate the painful sensation. Although the thermode is computer-controlled, it may potentially produce hot temperatures, which causes pain. In this case, the subjects are allowed to withdraw their arm from a thermode. The Medoc analysis station controls and monitors the thermode temperature for the TSA-II. This software has a built in safety feature, which has an automatic shut-off if the thermode reaches 50°C. This build-in shut-off, along with the ability for the investigator to monitor the thermode's temperature in real-time makes the chance of even superficial burns occurring minimal. Several large multicenter studies have safely used identical equipment and test paradigms without the occurrence of adverse events^{39,44,46,47}.

- 4. Sensory testing of mechanical pain thresholds.** Mechanical pain thresholds will be assessed with 7 weighted pinprick stimulators in accordance with the manufacturer's directions. The assessment is associated with mild pain, but since we only assess the pain perception threshold (i.e. the first pin at which pain is experienced) the pain only persists for a few seconds. The pinprick stimulators do not penetrate the epidermis on normal skin. However, as a precautionary measure the pinprick stimulator tips are sterilized with 70% ethanol prior to each new test session. Several large multicenter studies have safely used identical equipment and test paradigms without the occurrence of adverse events^{39,44,46,47}.

5. Topical administration of ketamine, amitriptyline and lidocaine.

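### The seven listed pinprick forces double at every step except 6.4 to 128 mN, a 20-fold jump; the list, range and starting force need checking against the actual pins before the mechanical pain threshold is scored

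*Combined protocol and SAP*

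**What the plan says.** Section 10 (Procedures Involved), under mechanical pain thresholds, describes the instrument: "This set consists of 7 pins with exponentially increasing force increments from 0.8 mN to 512 mN". It then gives the individual forces as "0.8, 1.6, 3.2, 6.4, 128, 256, and 512 mN". The lightest pin is stated again in the testing instruction: "Starting with the lightest (0.8 mN), each stimulator is applied in an ascending/descending order". The score is defined there too: "The final threshold is the geometric mean of five series of ascending and descending stimuli". The same paragraph refers to a published sensory-testing protocol for the method.

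Section 14 (Risks to Subjects), item 4, repeats the number of pins but gives no forces: "Mechanical pain thresholds will be assessed with 7 weighted pinprick stimulators in accordance with the manufacturer's directions".

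Section 9 (Study Endpoints) places the measure among the exploratory outcomes, in force units: "Mechanical pain threshold (mN needed to perceive pain". Section 3 (Objectives) instead counts analgesic effects on mechanical stimuli among the secondary outcomes. No other part of the document lists the pin forces or explains the gap in the series.

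**The concern.** A set described as exponentially increasing should have a roughly constant ratio between neighbouring pins. Five of the six printed steps have a ratio of 2 and one has a ratio of 20, so the list does not match its own description.

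This is operative text. The list is the only key in the documents from pin to millinewtons, for an outcome that is reported in millinewtons and scored as a geometric mean of pin forces. If the printed numbers were used for scoring and were not the true forces, thresholds would be mis-scaled by an amount that depends on which pins a subject reaches. A topical analgesic is expected to raise the threshold. A rise that crosses the break would therefore look much larger than it was.

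**Working it through.** **Inputs.** Printed forces, number of pins (7), range (0.8 to 512 mN) and scoring rule (geometric mean of five ascending and descending series), all from section 10. Assumption: each ascending and each descending run yields one turning value, so 5 + 5 = 10 values per site.

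**1. Ratios of neighbouring forces.**
1.6/0.8 = 2; 3.2/1.6 = 2; 6.4/3.2 = 2; 128/6.4 = 20; 256/128 = 2; 512/256 = 2.

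**2. Can any regular seven-pin series run from 0.8 to 512?**
- Doubling up from 0.8: 0.8, 1.6, 3.2, 6.4, 12.8, 25.6, 51.2. It ends at 51.2, not 512.
- Doubling down from 512: 512, 256, 128, 64, 32, 16, 8. It starts at 8, not 0.8.
- Doubling all the way from 0.8 to 512 would need 1 + log2(512/0.8) = 1 + log2(640) = 10.3 pins.
- A constant ratio over seven pins would be 640^(1/6) = 2.94, giving 0.8, 2.35, 6.89, 20.2, 59.4, 174, 512. None of the five printed values between the ends appears.

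The stated description is therefore not reproduced. Two doubling series each fit part of the text: 8–512 keeps the upper three values, and 0.8–51.2 keeps the lower four.

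**3. Effect on the threshold if the printed values are used.** With k of 10 turning values at pin 4 and the rest at pin 5, MPT = (F4^k × F5^(10−k))^(1/10):

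| Pin 4 / pin 5 | Printed list | 8–512 set | 0.8–51.2 set |
|---|---|---|---|
| 10 / 0 | 6.4 | 64.0 | 6.4 |
| 8 / 2 | 11.65 | 73.52 | 7.35 |
| 5 / 5 | 28.62 | 90.51 | 9.05 |
| 2 / 8 | 70.31 | 111.43 | 11.14 |
| 0 / 10 | 128 | 128 | 12.8 |

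For the even split, √(6.4 × 128) = 28.6, √(64 × 128) = 90.5 and √(6.4 × 12.8) = 9.05. The printed list is then 90.5/28.6 = 3.2 times too low on one reading and 28.6/9.05 = 3.2 times too high on the other. Across the table the error runs from none to 10-fold.

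**4. Effect on the contrast with vehicle.** If every turning value moves from pin 4 to pin 5, the printed list records 128/6.4 = 20-fold, log10(20) = 1.30. Either doubling set records 2-fold, log10(2) = 0.30. If only half of them move, the recorded ratios are √20 = 4.47 and √2 = 1.41.

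**5. When the error cancels.** If all turning values at both sites lie on one side of the break, any scale error is a common factor and drops out of the ratio: pin 2 to pin 3 is 3.2/1.6 = 2 as printed and 32/16 = 2 on the 8–512 set. It does not drop out of a raw difference (1.6 mN against 16 mN). When values straddle the break, the ratio is also distorted, unless both sites happen to have the same share of values below it.

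**The case against.** The strongest objection is that the list may never be used for scoring. It sits in a description of a commercial, standardized set; section 10 refers to a published method and section 14 to the manufacturer's directions. Nothing says the parenthetical list is the scoring key. If staff record the force marked on each physical pin, every MPT value is right and only the text is wrong. This stands, and it makes the consequence conditional. It does not remove the contradiction, because these are the only forces the documents give.

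A second objection concerns direction. A reader might infer that the lower four values are ten-fold too small, so that the alternating subject's threshold is 1 − 28.6/90.5 = 68% too low. The documents do not support that inference. The low end, 0.8, is printed in the range, the list and the starting instruction; the high end, 512, in the range and the list. Either correction changes several numbers, and choosing between them needs the pins themselves or sources outside the documents.

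Third, the 20-fold figure is the extreme case, because it needs every turning value to move. Partial movement gives less, and subjects who stay on one side of the break are compared correctly as a ratio. This also stands.

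A fourth possibility is that the printed forces are real. Thresholds would then not be mis-scaled, but no pin would lie between 6.4 and 128 mN, nothing in that interval could be resolved, and the description as an exponential series would still be misleading.

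**Conclusion.** The inconsistency is certain: the printed forces contain one 20-fold step in a series that otherwise doubles, and no regular seven-pin series with the stated ends matches them. Either the lower four or the upper three values, with the matching end of the range, appear to be off by a factor of ten. Which of the two cannot be settled from the documents.

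The effect on data depends on two conditions: that MPT is scored with the printed values, and that those are not the true forces. If both hold, single thresholds are wrong by anything from nothing to 10-fold, in a direction that depends on which end is wrong. A full pin 4 to pin 5 shift is recorded as 20-fold instead of 2-fold, and that holds for either doubling set. It would go too far to conclude that the trial's MPT results will be wrong.

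The reach is limited. Section 9 makes MPT exploratory, although section 3 ranks mechanical analgesia as secondary. The primary itch AUC, the itch-based secondary endpoints in section 9 and the sample size do not use pin forces. The point should be settled before MPT is scored, but it does not threaten the trial's main conclusion.

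**What to change.** Before any MPT is scored, read the force marked on each of the seven pins in the set actually used. Correct three places in section 10 to match: the list, the stated range and the force of the lightest pin. State that the geometric mean is computed from those marked forces. If the marked forces turn out to equal the printed ones, keep the list, drop the description of an exponential series, and note that thresholds between 6.4 and 128 mN cannot be resolved. If any thresholds have already been scored, confirm which forces were entered; where the pin reached was recorded, they can be rescored without retesting. The cost is a look at seven pins, a short text correction and a check of any values already entered. It adds no visits, no subjects and no change to the analysis.

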- 5) Currently enrolled in any investigational study in which the subject is receiving any type of drug, biological, or non-drug therapy.
- 6) Use of oral, topical analgesics, or other medications known to interfere with itch or pain perception 48 hours prior to the study visits (e.g. antihistamines, anesthetics, anti-inflammatories, opioids, neuroleptics, etc.).

- 7) Use of emollients on the volar aspects of the forearms arms on the day of the study visit.
- 8) Use of anti-depressants, anti-psychotics, and illicit drugs.
- 9) Known history of neuropathy, uremia, uncontrolled thyroid disease, and diabetes mellitus.
- 10) Known history of anaphylactic shock, or allergy to cowhage and/or known adverse reactions to lidocaine (or other local anesthetics of the amide type), ketamine or amitriptyline.
- 11) Pregnant (females of childbearing potential will undergo an hCG pregnancy test).
- 12) Currently incarcerated.

6) Number of Subjects*

A priori power calculations were conducted in G*Power based on data from a previous test-retest study³⁸. In order to have an effect 80% power with a size effect of 0.30 and alpha error probability of 0.05, we will need 36 subjects (10 within post hoc pairwise comparisons). We estimate that we will need to screen up to 42 individuals in order to enroll 36 healthy subjects.

We will seek to recruit a sample with an approximately equal gender distribution.

7) Study-Wide Recruitment Methods*

IRB approved flyers will also be placed around the University of Miami medical campus, and within the waiting rooms of the Department of Dermatology Out Patient Clinic at UMH (South Building, suites K-M) and at the Lennar Foundation Medical Center.

8) Study Timelines*

This projected is expected to last 8 months. The first 6 months will be dedicated to subject enrollment. During this time each subject will be a part of 2 study visits; one session lasting approximately 2.75 hours and one lasting approximately 2 hours. The second session must be completed within 7 days of the first session. The second 2 months will be dedicated to the sample analysis and the last month will be dedicated to dissemination of findings.

9) **Study Endpoints***

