Statistical Analysis: Data will be entered into a database program, such as Microsoft Excel and/or IBM SPSS, and analyzed at using Prism GraphPad 6 and/or IBM SPSS. Basic descriptive statistics using mean (SEM), range, and n (%) will be calculated in Excel and presented. Statistical significance will be set at $p < 0.05$. Analysis will be performed within and between groups.

Normality assessment will be tested by visual inspection and Shapiro-Wilks tests. A repeated measure (between–within) ANOVA will be used for the main analysis and post hoc comparisons will be conducted using the Bonferroni correction in a manner similar to Dunnett’s test.

Blinding procedures: The study will be conducted under double-blinded conditions. The investigators responsible for the data collection, i.e. application, sensory tests, itch provocations, and data entry, will be blinded to the substance being applied. Blinding will be carried out by random allocation of letters “A” to “E” to labels on the pharmaceuticals (including the vehicle). This task is carried out at the compounding pharmacy. With delivery of the pharmaceuticals a list specifying the compounds corresponding to allocated letters is supplied to the PI. In case of serious adverse effects, the PI will breach the blinding. Otherwise unblinding will not occur until after the primary analysis has been conducted.

Local safety assessment: After pretreatment with each ointment (before any sensory testing is performed), and after each cowhage application a local safety assessment will be done. Erythema, edema, and any other local reaction will be recorded on a 5-point Likert scale (0=clear, 1=almost clear, 2=mild, 3=moderate, 4=severe).

11) **Data Management***

All of the data, including records of subjects, source documents, and informed consent will be kept in the study center office under lock for 6 years after the study finished. The study center office is located at: [name].

12) **Provisions to Monitor the Data to Ensure the Safety of Subjects***

The study team will be responsible for protecting the safety, rights, and well-being of study participants. When testing is performed the subjects' vital signs (blood pressure, heart rate, and respiratory rate) will be monitored.

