Recording and reporting of adverse events that occur during the course of the study will help to ensure the continuing safety of participants. Local and systemic adverse events will be monitored during the study. Dermatologic evaluations for rash, erythema (outside of administration area), urticaria, eruptions, and epidermal necrolysis will be performed throughout the study visit. Anaphylaxis and hypersensitivity (erythema multiforme) will also be monitored for.

Study subjects will be instructed to report any adverse events up to one week after the study is completed. In case an adverse event does take place, a documentation system will be used to record the following information: description of event, time/date of onset, duration of reaction, dose/frequency/route of drug administration, reversibility or sequelae,

therapy (if any), and seriousness/severity (based on Common Terminology Criteria for Adverse Events v4). If a subject experiences an adverse event assessed at \geq Grade 2 according to CTCAE v4, the subject will not receive additional treatments and will be followed until the adverse event resolves or stabilizes.

Study stoppage will occur if 36 subjects complete the study or if a severe adverse event occurs.

The PI will be responsible for monitoring ongoing activities to ensure compliance with regulator and protocol requirements, data quality, and participant safety.

13) **Withdrawal of Subjects***

All subjects are free to withdraw from participation in this study at any time, for any reason, and without prejudice.

Subjects must be withdrawn from the study if:

- 1) A subject withdraws consent.
- 2) The Investigator believes it is in the best interest of the subject to be removed from the study.
- 3) If the subject experiences greater than a mild adverse event. (Subjects that experience a mild adverse event will be asked if they would like to continue the study. The occurrence of a severe adverse event will trigger the study to stop for safety purposes.)

If withdrawal occurs, subjects will receive prorated compensation. The data collected before the withdrawal will still be used in data analysis.

14) **Risks to Subjects***

1. **Discomfort.** The researchers will take care to minimize discomfort and pain during the measurement of pain thresholds and cowhage application. These procedures are already designed to limit magnitude and duration of discomfort.

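### The main ANOVA is labelled between–within without a between-subject factor, and in its classical form it drops subjects who have only the three visit-1 treatments; a mixed model would use them at little cost

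*Combined protocol and SAP*

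**What the plan says.** The Statistical Analysis paragraph of section 10 gives the method in one line: "A repeated measure (between–within) ANOVA will be used for the main analysis". Just before it comes "Analysis will be performed within and between groups". Neither sentence lists a factor or defines a group.

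The rest of section 10 assigns all five products to each subject: three randomly chosen at visit 1 and the other two at visit 2, with sites and order also randomised. The only subject-level split mentioned is sex, as a recruitment aim in sections 5 and 6: "We will seek to recruit a sample with an approximately equal gender distribution". No endpoint in section 9 uses it.

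Subjects with an incomplete set of treatments are foreseen. Section 12 says that after an adverse event of Grade 2 or higher "the subject will not receive additional treatments and will be followed until the adverse event resolves or stabilizes", and section 13 provides for withdrawal. On such subjects, section 13 states: "The data collected before the withdrawal will still be used in data analysis". It does not say in which analysis. No mixed model, imputation, available-pair rule or analysis population is named anywhere.

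On numbers, section 6 says "We estimate that we will need to screen up to 42 individuals in order to enroll 36 healthy subjects", while section 12 says "Study stoppage will occur if 36 subjects complete the study".

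**The concern.** A between–within ANOVA needs a factor on which subjects differ. None is given, so the between part has no defined meaning.

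The more practical matter is who enters the main analysis. A classical repeated-measures ANOVA needs all five cells per subject, so a subject who stops after visit 1 contributes nothing, even if both vehicle and KeAmLi were tested. One analyst could drop these subjects, a second could keep the available vehicle/KeAmLi pairs, and a third could fit a mixed model. Each could claim to follow the plan for the primary contrast. At stake are some precision in that contrast and a choice left open until after the data are seen.

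**Working it through.** **The plan's own figure.** The 36 in section 6 (80% power, effect size 0.30, alpha 0.05) cannot be reproduced uniquely, because the test family, number of groups and measurements, correlation, epsilon and effect-size metric are not stated. Reading 0.30 as Cohen's f with one group, five measurements and sphericity gives N = 15 at correlation 0.5 and N = 28 at correlation 0. Some layouts with groups do give 36 (for example an interaction test with 4 groups, 2 measurements and correlation 0.5), but the protocol describes no such groups. Nothing below depends on how 36 was obtained.

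**Inputs from the documents.** 36 subjects; five treatments split 3 then 2 at random; primary contrast KeAmLi minus vehicle on itch AUC.

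**Assumptions.** The documents give no loss rate, correlation or visit shift. I take a subject intraclass correlation of 0.3, 0.5 or 0.7, and 2, 4 or 6 subjects lost at random after visit 1.

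**What a visit-1-only subject contributes.** There are C(5,3) = 10 possible visit-1 sets. Both vehicle and KeAmLi are in 3 of them, exactly one in 6, and neither in 1. A complete-case ANOVA uses none of these subjects.

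**Variance of the contrast relative to 36 complete subjects.** Complete cases: 36/(36 − k). Mixed model: generalised least squares with treatment and visit as fixed effects and a random subject effect, averaged over random designs.

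| Partial subjects | Not replaced: complete cases | Not replaced: mixed model | 36 completers plus partial subjects: mixed model |
|---|---|---|---|
| 0 | 1.00 | 1.007 | 1.007 |
| 2 | 36/34 = 1.059 | 1.034–1.036 | 0.978–0.979 |
| 4 | 36/32 = 1.125 | 1.062–1.066 | 0.950–0.954 |
| 6 | 36/30 = 1.200 | 1.093–1.099 | 0.924–0.928 |

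Ranges are over the three correlations. In the last column the complete-case comparator is 1.00. With 4 lost and not replaced, the standard error rises by √1.125 − 1 = 6.1% for complete cases and by about √1.065 − 1 = 3.2% for the mixed model, equivalent to 32 against 36/1.065 = 33.8 pairs. An available-pair rule would give 32 + 0.3 × 4 = 33.2 expected pairs.

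**Visit term.** Vehicle and KeAmLi fall in different visits for 6/10 of subjects, in either direction equally often. A visit shift of δ (in SDs of the paired difference) that is left out of the model therefore adds 0.6δ² to the variance: 0.6 × 0.25² = 3.75%, or 0.6 × 0.5² = 15%. It adds no bias, because treatments are randomised to visits. The term costs 0.7% when there is no shift and breaks even at √(0.007/0.6) = 0.11 SD.

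**Subject-by-visit effect.** If a subject's ratings are more alike within a visit than across visits, a random subject effect alone wastes information. For illustration, assume variances of 0.3 (subject), 0.3 (subject-by-visit) and 0.4 (residual), with nobody lost. The contrast variance is then about 0.83 with the extra term, against about 1.00 with a subject effect alone. The table does not include this term.

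**Order and site terms.** Adding both raises the mixed-model figures, without replacement, to about 1.045, 1.075, 1.11 and 1.14 for 0, 2, 4 and 6 lost. That nearly cancels the gain at 4 lost and is worse than complete cases at 0 or 2.

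**Validity under loss at random.** A simulation (correlation 0.5; 0 or 4 lost; visit shift 0 or 0.5 SD) showed no material bias in either method. Type I error was 0.048–0.053 for the ANOVA contrast and 0.045–0.055 for the mixed model.

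**The case against.** The strongest reply is that section 12 ends the study on 36 completers. On its plain reading lost subjects are replaced, the complete-case ANOVA keeps all 36, and what is forgone is only the 2–7% gain. This stands as the likelier reading, but section 6 speaks of enrolling 36, and its allowance of 42 is for screening, so the replacement rule should be stated.

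Second, *between groups* may simply mean between treatment conditions, and the primary contrast is fixed in sections 3 and 9. This also stands: that part is mostly wording, and no effect on the primary contrast has been shown.

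Third, the section 13 sentence on retained data could be met by descriptive statistics. It could. A reader might infer that the plan promises to put partial subjects in the main analysis and so contradicts itself, but the text does not go that far. Similarly, section 8 says "The second session must be completed within 7 days of the first session" without saying that late data are excluded, so this is only a possible source of partial subjects.

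Fourth, one sentence defining the analysis set, or an available-pair rule, would settle the ambiguity. True, but with 4 lost it would keep 33.2 expected pairs against about 33.8, and it would leave visit unmodelled.

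**Conclusion.** The point holds as a minor one. The plan names a design label that does not fit and a method that, in its classical form, sets aside data it says will be used. A better method is available at almost no cost. The gain is about 2%, 5% or 7% of variance if withdrawn subjects are replaced. If they are not, the rise in variance is roughly halved. These figures rest on the assumed correlations, on loss at random, and on a model with a random subject effect only.

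Two stronger readings should be resisted. A reader might infer that the trial loses substantial power; that needs non-replacement, which the stop at 36 completers argues against. A reader might also infer that the primary test is biased or its type I error inflated. Leaving out visit, order and site does not bias the contrast, because treatments are randomised to them.

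Nor is precision shown to be the only cost. Subjects are withdrawn for adverse events, which could depend on what was applied at visit 1, so loss may not be random. For partial subjects the absence of bias is an assumption under either analysis, and the mixed model relies on data being missing at random.

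**What to change.** 1. Delete the between–within label and the reference to between groups, or name the between-subject factor intended.
2. Make the main analysis of itch AUC a linear mixed model on all observed provocations, with fixed effects for treatment and visit, a random subject effect and a subject-by-visit effect (dropped if estimated as zero). Name KeAmLi minus vehicle as the primary contrast.
3. State that the model assumes data are missing at random, note that adverse-event withdrawal may not satisfy this, and report a complete-case sensitivity analysis.
4. Reconcile enrolling 36 (section 6) with stopping when 36 complete (section 12) by stating whether withdrawn subjects are replaced.
5. Keep order and site terms, if wanted, for a sensitivity analysis.

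The cost is wording. The planned 36, the visits and the procedures are unchanged, and IBM SPSS, already listed, can fit the model. With no loss and no visit shift, the visit term costs about 0.7% in variance; adding order and site to the main model would bring this to about 4.5%.
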